5.1.3 PH94B

PH94B (3 β -androsta-4,16-dien-3-ol) is a synthetic neuroactive steroid discovered and initially developed at Pherin Pharmaceuticals that targets human nasal chemosensory cells^{11,36} and has been demonstrated in Phase 2 clinical trials to have benefits for the acute treatment of SAD.⁴⁰

Pherines induce calcium ion entry in human nasal chemosensory neurons.^{37,41} Pherines such as PH94B target G-protein-coupled receptors that are expressed in human nasal chemosensory neurons.^{32,42}

AD-MW-07.08 18-Jun-2019 Page 23 of 101

In vitro screening studies using isolated, living, human nasal chemosensory neurons have shown that picomolar quantities of PH94B can selectively induce inward currents in a concentration-dependent and reversible fashion. These membrane currents are carried by calcium ions. In institutional review board (IRB)-approved studies, pulsatile intranasal (i.n.) administration of nanogram quantities of airborne PH94B to human subjects induced dose-dependent depolarization of the electrogram recorded from the surface nasal chemosensory mucosa, which is a measure of the local mass receptor potential response.

PH94B exerts its activity by stimulation of neural circuits involving the limbic amygdala, and it does not require systemic uptake and distribution to produce its anxiolytic pharmacological effect. PH94B is being investigated as a potential acute treatment for the alleviation of anxiety symptoms in adult patients with SAD. While PH94B may regulate gamma aminobutyric acid circuits in the limbic amygdala, electrophysiological experiments in vitro showed that PH94B does not directly bind to or modulate gamma aminobutyric acid receptors at concentrations of 10 μM or lower, which differentiates its mechanism of action from benzodiazepines.⁴⁴

5.2. Clinical Experience

5.2.1 Phase 1 Studies

PRODUCTION FRANCISCO CONTRACTOR C	

5.2.2 Phase 2 Studies

Two previously completed Phase 2 clinical studies have enrolled similar populations and had similar efficacy endpoints to Protocol PH94B-CL026. These double-blind, randomized, placebo-controlled Phase 2 clinical studies () included a total of

12-Aug-2022 Amendment 3, Version 4.0

AD-MW-07.08 18-Jun-2019

Protocol PH94B-CL032

91 female subjects who met criteria for SAD (generalized subtype) as defined by the Diagnostic and Statistical Manual of Mental Disorders, 4th Edition. PH94B (1.6 µg) was administered i.n. in spray form to both a performance (public speaking) challenge and a social interaction challenge simulation which took place at the clinical sites.

The primary outcome measures were the Clinical Global Impression Scale of Improvement (CGI-I) and the Subjective Units of Distress Scale (SUDS). The SUDS scores range from 0 to 100, with higher scores indicating greater levels of anxiety. Subjects receiving PH94B were more likely than those who received placebo to show improvement on the CGI-I following treatment. In the PH94B group, 34 of 45 subjects (75.6%) were rated very much less anxious or much less anxious compared to only 17 of 46 subjects (37%) in the placebo group. A test for the difference between proportions indicated a Z value of 4.03, p = 0.0001 (Fisher's exact test).

During the public speaking challenge, subjects randomized to PH94B (n=45) showed an improvement of 26.7 points in the mean score on the SUDS at Visit 3 (initial treatment visit) as compared to Visit 2 (baseline visit, at which all subjects received placebo). In comparison, subjects randomized to placebo (n=46) showed an improvement of only 14.0 in the mean SUDS score across visits. The PH94B group's improvement from Visit 2 to Visit 3 significantly exceeded the placebo group's improvement from Visit 2 to Visit 3 (t = 3.16, p = 0.002) on this challenge. No SAEs were reported, and no subjects were terminated prematurely from the study due to AEs.

5.3. Summary of Potential Risks and Benefits

There are no direct benefits to participation for subjects in this study. Subjects will receive a single i.n. dose of PH94B or placebo at the study site. PH94B is intended for acute treatment of SAD, and the activity is not expected to last long beyond the subjects' study visit.

Based on previous clinical studies conducted with PH94B, it is believed to be safe and well tolerated, and risks to subjects are considered minimal. Intranasal administration of PH94B may increase the risk of local site reactions including itching, burning, runny nose, sneezing and soreness inside the nose. In completed clinical studies, the most commonly reported AE was headache. None of these effects was reported in more subjects receiving PH94B than in subjects receiving placebo.

A summary of the pharmaceutical properties and known potential risks of PH94B is provided in the current version of the investigator brochure (IB). The investigator must become familiar with all sections of the PH94B IB before the start of the study.

AD-MW-07.08 18-Jun-2019 Page 25 of 101

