7.2. Rationale and Discussion of Study Design

The present study employs a randomized, double-blind, placebo-controlled, parallel design, which is generally considered to be the gold-standard for clinical trials. The use of a placebo for the study comparator is based on the absence of an active comparator that could be delivered by the i.n. route, which is essential for maintaining the study blind.

The study will use a public speaking challenge to provoke anxiety in participating subjects, who will rate their anxiety subjectively using the SUDS, which are both commonly used in clinical studies of SAD. Additional subjective evaluations include the PGI-C scale and Other evaluations include the CGI-I, performed by the Investigator and a trained observer.

Safety assessments are standard for the evaluation of an investigational medicinal product, and include collection of AEs and SAEs, and evaluation of vital signs, safety laboratory tests, suicidality and level of depression, ECGs, and physical examinations; given the use of the i.n. route of administration, the physical examination will include an examination of the nasal passages. Given that subjects are patients with a confirmed diagnosis of SAD, the C-SSRS will be used at each study visit as a precautionary measure.

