13.1.5.1 Adverse Events

All AEs will be coded using the most recent version of MedDRA.

Treatment-emergent AEs are defined as:

- AEs with onset at the time of or following the start of treatment with IP through the Follow-up Visit or
- AEs starting prior to the start of treatment but increasing in severity or relationship at the time of, or following, the start of treatment with IP through the Follow-up Visit.

AD-MW-07.08 18-Jun-2019 Page 65 of 101

Amendment 3, Version 4.0

Adverse events will be classified by time of occurrence and Visit 3 group assignment to more clearly identify those arising after exposure to placebo only and those arising after exposure to PH94B.

The number and percentage of subjects with AEs will be displayed for each treatment group by system organ class and preferred term. Summaries of AEs by severity and relationship to IP will also be provided. Serious adverse events and AEs resulting in discontinuation of IP will be summarized separately in a similar manner. Subject listings of AEs, SAEs, and AEs causing discontinuation of IP will be produced.

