2.2.2. Safety Endpoints

The safety endpoints are mapped to the safety objective as follows:

Safety Objective

The safety objective of the study is to determine safety and tolerability of PH94B compared to placebo in adult subjects with SAD from reported AEs and changes in vital signs, 12-lead ECGs, laboratory parameters, suicidality, level of depression, and physical examinations.

Safety Endpoints

Incidence and severity of AEs

Changes in vital signs results

Changes in clinical laboratory evaluation (hematology, chemistry, and urinalysis) results

Changes in 12-lead ECG results

Changes in physical examination findings

[figure not shown]
Mean HAM-D scores

[figure not shown]
Incidence of treatment-emergent suicidal ideation and behavior

3. Overall Study Design and Plan

3.1. **Overall Design**

The study is a Phase 3, multicenter, randomized, double-blind, placebo-controlled, parallel design, single-dose, clinical trial of the efficacy, safety, and tolerability of the acute administration of PH94B to relieve symptoms of acute anxiety in adult subjects with SAD.

Efficacy assessments for the primary endpoint will be completed at Visit 2 (Baseline) and Visit 3 (Treatment). Efficacy assessments for the secondary endpoint will be completed at Visit 3 (Treatment). Safety assessments are completed at Visit 1 (Screening) and Visit 4 (Follow-Up), with the exception of vital signs assessments, pregnancy tests, and Columbia-Suicide Severity Rating Scale (C-SSRS), which are completed at all visits, and AE recordings, which are completed starting at Visit 2 (Baseline). Refer to the Schedule of Events (Table 1) for more detail.

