An overall summary of TEAEs will be provided; this will present number and percent of subjects who reported at least 1 of the following: TEAE (including any TEAE, TEAEs by maximum severity, and related TEAEs), TEAE leading to discontinuation of the study drug, TEAE leading to discontinuation from the study, serious TEAEs, and SAEs leading to death.

In addition to the overall summary, summaries of the number and percentage of subjects with TEAEs will be displayed for each treatment group by SOC and preferred term. Summaries of TEAEs by severity (Severe > Moderate > Mild) and relationship to IP (Related > Not Related) will also be provided. Serious TEAEs and TEAEs resulting in discontinuation of IP will be summarized separately in a similar manner.

Subject listings of AEs, SAEs, and AEs causing discontinuation of IP will be produced. Adverse events that are treatment emergent will be flagged.

The AE summary tables will include counts of subjects. Therefore, if a subject experiences more

than 1 episode of a particular AE, the subject will be counted only once for that event. If a subject has more than 1 AE that is coded to the same preferred term, the subject will be counted only once for that preferred term. Similarly, if a subject has more than 1 AE within an SOC, the subject will be counted only once in that SOC. This will be handled separately for each time period (Before Visit 3 Dosing and During or After Visit 3 Dosing).

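### No planned safety row compares the arms on subjects with at least one local nasal reaction, the harm that Protocol 5.3 says intranasal PH94B may increase

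*Protocol*

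**What the plan says.** Protocol 5.3 describes the local risk in these words: "Intranasal administration of PH94B may increase the risk of local site reactions including itching, burning, runny nose, sneezing and soreness inside the nose". In the visible text this is the only harm that PH94B is said to be able to increase. The section then qualifies it for completed studies, after also naming headache: "None of these effects was reported in more subjects receiving PH94B than in subjects receiving placebo".

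The safety objective (Protocol 6.2, SAP 2.1.2) is comparative: tolerability of PH94B against placebo.

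On tabulation, Protocol 13.1.5.1 says: "The number and percentage of subjects with AEs will be displayed for each treatment group by system organ class and preferred term". SAP 9.1 gives an overall TEAE table, and beyond that "summaries of the number and percentage of subjects with TEAEs will be displayed for each treatment group by SOC and preferred term". Further tables split the same rows by severity and by relationship. Everything is shown separately for the periods before, and during or after, Visit 3 dosing. Within a period, "if a subject has more than 1 AE within an SOC, the subject will be counted only once in that SOC". The planned tables (14.3.1.1 to 14.3.1.4) follow this scheme. The visible text has no grouped local-reaction row and no adverse event of special interest.

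Collection is explicit. Protocol 11.2 requires local reactions to be captured in the eCRF. Section 10.2.3 has adverse events reviewed after the Visit 3 challenge, and Section 10.2.4 has them reviewed again at Visit 4.

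**The concern.** The five symptoms in Section 5.3 are different expressions of one harm. If each is coded to its own preferred term, a modest excess can appear as several rows of one to three subjects per arm, none of which looks different. The per-subject total cannot be recovered by adding those rows, because one subject can appear in several. The SOC row avoids double counting, but it mixes in unrelated events from the same class and helps fully only if all five symptoms fall in one class.

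What is at stake is how sharply the report can speak on the named local risk. That applies in both directions: a grouped row shows an excess more clearly if there is one, and better supports a statement of no excess if there is none.

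**Working it through.** The plan gives no figure for local reactions to reproduce. It states neither rates nor durations, and safety is descriptive (SAP Section 9). What follows illustrates how much information each type of row carries; it is not a claim about PH94B.

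**Inputs**
- n = 104 per arm (SAP 3.2).
- Five symptoms (Protocol 5.3).
- Assumed: each symptom occurs in 3% of PH94B and 1% of placebo subjects, independently within a subject. For the SOC row, all five are assumed to share one SOC, with unrelated events in a share b of both arms.

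**Formulas**
- Grouped incidence: g = 1 − (1 − p)^5.
- SOC incidence: s = 1 − (1 − g)(1 − b).
- Chance of excluding zero: full binomial enumeration of the two-sided 5% z-test with pooled variance.

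**Rates and expected counts**
- Single term: 104 × 0.03 = 3.1 against 104 × 0.01 = 1.0 subjects.
- Grouped: 1 − 0.97^5 = 14.1% against 1 − 0.99^5 = 4.9%, or 14.7 against 5.1 subjects.
- SOC row: 15.8% against 6.8% at b = 2%; 18.4% against 9.7% at b = 5%; 22.7% against 14.4% at b = 10%.

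| Row | Chance of excluding zero |
|---|---|
| Single preferred term | 15% |
| SOC, b = 10% | 34% |
| SOC, b = 5% | 45% |
| SOC, b = 2% | 56% |
| Grouped local reaction | 65% |

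**Intervals at typical counts** (95% Newcombe)
- 3/104 against 1/104: difference 1.9 points, −2.8 to 7.2.
- 15/104 against 5/104: difference 9.6 points, 1.5 to 18.1.

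**Sensitivity**
- Judged by the Newcombe interval instead of the z-test, the single-term and grouped chances are about 9% and 62%.
- Other assumed rates, z-test, single term and grouped: 2% against 0.5% gives 9% and 60%; 2% against 1% gives 6% and 26%.
- Symptoms that do not overlap, totalling 15% against 5% (normal approximation): 0.18 for a single term and 0.67 grouped. With Fisher's exact test: 0.04 and 0.61.
- Correlated symptoms (Gaussian copula, 3% against 1% per term): the grouped chance falls from 65% to 47% at correlation 0.5 and to 32% at 0.8.

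**The case against.** A reader might infer that the plan hardly measures local reactions, or that its tables could not show an excess. The documents do not support that. Dosing is 20 minutes before the challenge (Protocol 9.2), so the review after the challenge falls soon after the dose. The SOC row counts each subject once. The any-TEAE and related-TEAE rows would also move. The adverse event listing is by subject, and listings are sorted by treatment (SAP 13.5), so the count could be rebuilt by hand. The fair comparator for a grouped row is therefore often the SOC row, and the gain is smaller than the single-term comparison suggests. All of this stands. What remains is that the SOC row is diluted by an unknown amount, and that a term list chosen after unblinding would be open to challenge.

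Section 5.3 also reports no excess in completed studies, and the placebo has the same excipients (Protocol 9.1), so reactions to the spray itself should affect both arms. That lowers the expected excess. It does not remove the statement that the risk may rise. The Phase 2 studies described in Section 5.2.2 gave 1.6 µg to 91 women, whereas this trial gives 3.2 µg to men and women.

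A reader might also infer that the nasal examination is mistimed. Protocol 7.2 explains that "given the use of the i.n. route of administration, the physical examination will include an examination of the nasal passages". SAP Table 1 and the visible visit lists place it only at Visits 1 and 4, so the one examination after PH94B comes 5 to 9 days after the dose. (The Visit 2 and 3 cells of that row in Protocol Table 2-1 are unreadable in the extracted text.) This does not show a defect. Itching, burning and soreness are mainly reported symptoms, which the adverse event review covers. The documents give no duration for local reactions. The remark that "the activity is not expected to last long beyond the subjects' study visit" concerns the acute anxiolytic effect. No extra examination is proposed here.

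**Conclusion.** The point holds as a gap in tabulation. The events are collected, but no planned row compares the arms on subjects with at least one local nasal reaction, and the SOC row is only a partial substitute. Under the assumed 3% against 1%, a grouped row raises the chance of excluding zero from 15% (single term), or from 34% to 56% (SOC row with 10% to 2% unrelated events), to about 65%. These figures rest on assumed rates, independence and, for the SOC row, a shared class. Correlation among symptoms would narrow the gain, and symptoms spread over several SOCs would widen it relative to the SOC row. The adverse event collection is not at fault, and nothing here implies that PH94B causes an excess.

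**What to change.** In SAP 9.1 and Table 14.3.1.1, add one descriptive row: *subjects with at least one local nasal reaction, onset during or after Visit 3 dosing*. Define it by a list of preferred terms covering the Section 5.3 reactions, fixed at the blinded data review meeting already planned in SAP Section 5. Show n and % by arm, and the PH94B minus placebo difference with a 95% Newcombe interval. No test is needed, so the safety analysis stays descriptive.

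The cost is one SAP sentence, a short term list and one table row, with no new data. The downside is that the local-reaction rate may look less favourable than the scattered single-term rows.

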6. OBJECTIVES

6.1. Primary Objective

The primary efficacy objective of the study is to evaluate whether the efficacy of PH94B to relieve acute anxiety induced during a public speaking challenge in adult subjects with SAD is greater than that of placebo as measured by the SUDS.

6.2. Secondary Objectives

The secondary efficacy objective of the study is to compare clinician-observed changes in subject response to an anxiety-provoking situation from Visit 2 to Visit 3 between PH94B-treated subjects and placebo-treated subjects, as measured by Clinical Global Impression - Improvement (CGI-I) scale.

The safety objective of the study is to determine safety and tolerability of PH94B compared to placebo in adult subjects with SAD from reported AEs and changes in vital signs, 12-lead electrocardiograms (ECGs), laboratory parameters, suicidality, level of depression, and physical examinations.

6.4. Endpoint Mapping

[figure not shown]
12-Aug-2022

Endpoints are mapped to study objectives as follows:

AD-MW-07.08 18-Jun-2019 Page 26 of 101

Objectives	Endpoints
Primary	
The primary efficacy objective of the study is to evaluate whether the efficacy of PH94B to relieve acute anxiety induced during a public speaking challenge in adult subjects with SAD is greater than that of placebo as measured by the SUDS.	The primary endpoint for the study is the difference in average SUDS score during the Visit 3 public speaking challenge versus the average SUDS scores during the Visit 2 public speaking challenge for PH94B compared to placebo.
Secondary	
The secondary efficacy objective of the study is to compare clinician-observed changes in subject response to an anxiety-provoking situation from Visit 2 to Visit 3 between PH94B-treated subjects and placebo-treated subjects, as measured by CGI-I.	The secondary efficacy endpoint in the study is the difference between proportions of PH94B-and placebo-treated groups in CGI-I scores of 1 or 2 recorded at the end of Visit 3 (Treatment).
The safety objective of the study is to determine safety and tolerability of PH94B compared to placebo in adult subjects with SAD from reported AEs and changes in vital signs, 12-lead ECGs, laboratory parameters, suicidality, level of depression, and physical examinations.	Incidence and severity of AEs Changes in vital signs results Changes in clinical laboratory evaluation (hematology, chemistry, and urinalysis) results Changes in 12-lead ECG results Changes in physical examination findings Mean HAM-D scores Incidence of treatment-emergent suicidal ideation and behavior

Amendment 3, Version 4.0 12-Aug-2022 Page 27 of 101 AD-MW-07.08 18-Jun-2019

7. STUDY DESIGN

7.1. Overall Study Design and Plan

The study is a Phase 3, multicenter, randomized, double-blind, placebo-controlled, parallel design group trial of the efficacy and safety of PH94B in the acute treatment of anxiety in adult subjects diagnosed with SAD as defined by the Diagnostic and Statistical Manual of Mental Disorders. 5th Edition and confirmed by the Mini International Neuropsychiatric Interview (MINI).

Subject participation in the study will last a total of 3 to 7 weeks, depending on the duration of the screening period and intervals between visits. Upon signing an informed consent form (ICF), all subjects will complete Visit 1 (Screening) and enter a screening period lasting between 3 and 35 days. If subjects meet all eligibility criteria at the end of the screening period, subjects will complete Visit 2 (Baseline), including participation in a 5-minute public speaking challenge (APPENDIX B)

Before and at every minute during the public speaking challenge, and at specified time points the subject will be asked for their SUDS score, which will be recorded by a trained observer.

At Visit 3 (Treatment), the subject will be allocated to receive treatment with The subject will self-administer randomly allocated investigational product (IP) and will then undergo a 5-minute public speaking challenge, with SUDS scores being collected before the challenge and at every minute during the challenge

At the end of the Visit 3 public speaking challenge, the subject will complete the PGI-C questionnaire, and the site personnel will complete the CGI-I assessment. One week (±2 days) after the completion of Visit 3, the subject will come back for Visit 4 (Follow-up), which will involve a repeat of the safety and psychiatric assessments conducted at Screening.

AD-MW-07.08 18-Jun-2019 Page 29 of 101

12-Aug-2022

Protocol PH94B-CL032

7.2. Rationale and Discussion of Study Design

The present study employs a randomized, double-blind, placebo-controlled, parallel design, which is generally considered to be the gold-standard for clinical trials. The use of a placebo for the study comparator is based on the absence of an active comparator that could be delivered by the i.n. route, which is essential for maintaining the study blind.

The study will use a public speaking challenge to provoke anxiety in participating subjects, who will rate their anxiety subjectively using the SUDS, which are both commonly used in clinical studies of SAD. Additional subjective evaluations include the PGI-C scale and Other evaluations include the CGI-I, performed by the Investigator and a trained observer.

Safety assessments are standard for the evaluation of an investigational medicinal product, and include collection of AEs and SAEs, and evaluation of vital signs, safety laboratory tests, suicidality and level of depression, ECGs, and physical examinations; given the use of the i.n. route of administration, the physical examination will include an examination of the nasal passages. Given that subjects are patients with a confirmed diagnosis of SAD, the C-SSRS will be used at each study visit as a precautionary measure.

